5.2 Endpoints

(ICH E9; 2.2.2)

Primary endpoint:

Proportion of subjects that remain on methotrexate with no intolerance one year after starting methotrexate. Intolerance is defined as ≥ 6 points in the English or French versions of the validated Methotrexate Intolerance Severity Score, MISS [1, 2]. The MISS questionnaire can be found in the appendix.

Secondary endpoints:

- 1) frequency and cumulative incidence of adverse events and any serious unexpected suspected adverse drug reactions (SUSARs).
- 2) the cumulative incidence of methotrexate intolerance within one year;
- 3) the cumulative incidence of attainment of inactive disease within one year defined by Wallace criteria [3] as modified by Guzman et al [4];
- 4) the cumulative incidence of starting a biologic medication within one year; and
- 5) the mean quality of life scores in the Quality of My Life scale 4-8 months after starting methotrexate [5];
- 6) the mean scores in the MISS questionnaire 4-8 months after starting methotrexate.

To enable future cost-effectiveness analysis, the EuroQol Collaboration 5-dimension scale for quality of life for youth parent-proxy questionnaire (EQ-5D-Y) is completed at every visit, for calculation of quality-adjusted life years [6], and medication costs will be calculated using the prices from the Ontario Drug Benefit Formulary [7].

Assessment of outcomes are completed at all clinic visits scheduled as per medical need using the CAPRI Registry (usual practice is every 1-4 months). OPT-JIA does not include additional trial-specific visits.

6 Study Methods

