6.4 Study Assessments

(ICH E3; 9.5.1. ICH E9; 2.2.2)

Visit	Baseline	Every Visit	Visit Month 12
History and examination	x	x	x
QOL questionnaire	x	x (\pm 14)	x (\pm 14)
MISS	x	x (\pm 14)	x (\pm 14)
Actionable AEs	x	x	x
SAEs	x	x	x
SUSARs	x	x	x
Concomitant medication	x	x	x
Methotrexate use and dose	x	x	x
Ondansetron use and dose	x	x	x

Analysis Time Windows

Visit (target day)	Lower bound (days)	Upper bound (days)
Baseline (0)	N/A	N/A
Every visit to clinic (time window not applicable)	N/A	N/A
Month 4-8 (180)	120	240
Month 12 (364)	308	420

7 Sample Size

(ICH E3; 9.7.2. ICH E9; 3.5)

Our primary outcome statistic is the ratio of two proportions (relative risk, RR): the proportion of randomized children remaining on methotrexate with no intolerance in the intervention group divided by the same in the control group. Our sample size calculation is based on expressing the RR in the log scale and using established formulas for standard errors [15, 16]. With $p<0.05$, power of 90% and expected methotrexate continuation with no intolerance of 50% in the control group and 75% in the intervention group the result is 79 evaluable subjects per group. We will aim to recruit 176 subjects total to allow for up to a 10% dropout rate.

8 General Analysis Considerations

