8.3 Covariates and Subgroups

(ICH E3; 9.7.1, 11.4.2.1. ICH E9; 5.7)

The following covariates at baseline will be used to define if post-randomization imbalances have occurred: age, sex, months since JIA diagnosis, JIA category, active joint count, physician global assessment of disease activity, parent global assessment of wellbeing, c-reactive protein level, erythrocyte sedimentation rate, body weight strata, previous treatment and presence of uveitis.

If imbalances have occurred ($p<0.1$), the imbalanced variables will be used in logistic regression models to adjust efficacy estimates. OPT-JIA does not include any subgroup analyses.

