9.5 Treatment Compliance

Compliance with ondansetron and methotrexate is queried at each medical visit by the attending physician (local investigator) and reported in the physician case report forms. Parents are asked to confirm in writing in the parents' questionnaire how many ondansetron tablets were given to their child with the previous dose of methotrexate.

Since this is a pragmatic trial to test effectiveness in usual medical practice, there will be no pill counts or measurement of blood medication levels as part of this trial.

10 Efficacy Analyses

The final efficacy analysis will be conducted after the last recruited trial participant has had an opportunity to be followed for 60 weeks from the date of recruitment (52 weeks plus an 8-week window of observation and data entry). The final dataset will then be verified and locked.

As per the OPT-JIA protocol (V3, 2-Sept-2020), the final analysis will be an intention to treat analysis including all randomized participants irrespective of whether they completed the trial, received or not the trial interventions, or dropped out. A secondary modified per-protocol analysis will be conducted on those subjects who received the assigned intervention for at least 3 months or stopped medications before 3 months for intolerance or toxicity.

All statistical analysis will test the null hypothesis of no differences between intervention and control groups. The a priori alternative hypothesis is that the intervention group will have better outcomes than the control group.

Logistic regression models will be used to adjust effect estimates for post-randomization imbalances in the two groups (intervention, control). Baseline variables with a p value <0.1 in the baseline comparison of intervention and control groups will be considered post-randomization imbalances and adjusted for, if any.

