Cumulative incidence of attainment of inactive disease within one year: The Kaplan Meier survival analysis estimate of the cumulative incidence of attainment of inactive disease within 52 weeks of study enrollment. At every visit to the clinic the pediatric rheumatologist is asked for current disease status (inactive disease = 1, active disease =2). Inactive disease is defined as per the Wallace criteria: no joints with active arthritis; no fever, rash, serositis, splenomegaly, or generalized lymphadenopathy attributable to JIA; no active uveitis (by SUN definition, <1 cell in field sizes of 1 mm by a 1-mm slit beam); ESR or CRP level within normal limits in the laboratory where tested or, if elevated, not attributable to JIA [If not tested because there was no clinical indication, it is assumed to be normal]; physician's global assessment of disease activity (PGA) score of best possible on the scale used (0 in a 21 point scale from 0=inactive to 10=very active disease); duration of morning stiffness of 15 minutes or less. Additionally: no enthesitis. Active disease means any of the above disease manifestations is present, or a PGA of 0.5 or more. Kaplan-Meier curves will be constructed separately for intervention and control groups and the curves will be compared using the log-rank test.

Cumulative incidence of starting a biologic medication within one year: The Kaplan Meier survival analysis estimate of the cumulative incidence of starting a biologic medication within 52 weeks of study enrollment. At every visit to the clinic the physician is asked if the patient is receiving any biologic medication (Yes = 1, No = 0). If the answer is yes, the physician selects the relevant medication from a list or enters the name of the medication. Kaplan-Meier curves will be constructed separately for intervention and control groups and the curves will be compared using the log-rank test.

Mean quality of life scores in the Quality of My Life scale 4-8 months after starting methotrexate: The arithmetic mean of the score in the Quality of My Life scale answered by the patient. If more than one score is available 4-8 months after enrollment, the score closest to 26 weeks is used. All patients considered mature enough to understand the questions (by their parents) are asked: "Some

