of the children who come to see us feel that their life is not that great, while others think that their life is O.K. How about you?" (The patient then selects the relevant answer in a 21-point horizontal rating scale from The worst = 0, to The Best = 10). Then, the patient is asked: "Considering my HEALTH, my life is..." and the patient again selects the relevant answer in a 21-point horizontal rating from The worst = 0, to The Best = 10). The answer to the second question is the score of interest. The mean scores of intervention and control groups will be compared with a two-sample two-tailed t-test.

Mean scores in the MISS questionnaire 4-8 months after starting methotrexate: The arithmetic mean of the score in the Methotrexate Intolerance Severity Score questionnaire answered by the parent. If more than one score is available 4-8 months after enrollment, the score closest to 26 weeks is used. The score is the sum of 12 items, each scored as 0= No complaints, 1= Mild, 2= Moderate, 3= Severe), for a total possible score of 36 points. The MISS questionnaire is included in the Case Report Forms appended to this Statistical Analysis Plan. The mean scores of intervention and control groups will be compared with a two-sample two-tailed t-test.

Mean scores and between groups p-values at 26 weeks are exploratory and will be interpreted with caution for two reasons: 1) OPT-JIA has no fixed-time visits and some patients may not have scores at 26 weeks; 2) The Quality of My Life score will not be available for patients deemed too young by their parents to understand the question.

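### The exploratory Quality of My Life comparison is an unadjusted t-test that makes no use of a baseline score that appears to be collected, and the SAP's only adjustment method cannot handle a continuous score.

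*SAP*

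**What the plan says.** Quality of My Life at 4-8 months belongs to objective 4 (SAP 5.1) and is secondary endpoint 5 (SAP 5.2). The score is the child's answer on a 0-10 scale about life considering health. Section 10.1 picks one value per child: "If more than one score is available 4-8 months after enrollment, the score closest to 26 weeks is used". The test follows: "The mean scores of intervention and control groups will be compared with a two-sample two-tailed t-test". Section 10.1 also calls the 26-week means and p-values exploratory, because some children will have no visit near 26 weeks and some are too young to answer.

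The schedule in section 6.4 has a row headed "QOL questionnaire", marked at baseline, at every visit and at month 12.

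Section 8.3 lists 12 baseline covariates to be checked for imbalance, beginning "age, sex, months since JIA diagnosis, JIA category, active joint count, physician global assessment of disease activity, parent global assessment of wellbeing". Baseline quality of life is not among them, nor is it in the baseline table of section 9.4 or in mock Table 1. For covariates with p<0.1, section 8.3 says "the imbalanced variables will be used in logistic regression models to adjust efficacy estimates", and the opening of section 10 repeats it: "Logistic regression models will be used to adjust effect estimates for post-randomization imbalances in the two groups".

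**The concern.** Children starting methotrexate differ in how they feel at entry, and part of that difference is likely to persist to six months. A comparison of follow-up means alone leaves this variation in the error term. It also lets any chance difference between arms at baseline carry over, in part, into the estimated effect. If the same scale is recorded at baseline, both costs can be reduced without new data.

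The plan's own safeguard does not reach this endpoint. Section 9 classes quality of life scores as continuous efficacy variables, and sections 8.3 and 10 promise to adjust efficacy estimates for imbalance. The only model they name is logistic regression, which does not estimate a difference in means on a 0-10 scale. So even a listed covariate that turns out imbalanced has no stated route into this estimate, and an imbalance in baseline Quality of My Life would not be looked for.

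At stake is the precision and readability of one secondary result.

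**Working it through.** **Inputs.** The planned size is 79 evaluable per group (SAP section 7). The SAP gives no SD, effect size or power for Quality of My Life, and no baseline-to-follow-up correlation r. I assume r of 0.3, 0.5 and 0.6. As a small-sample case I assume 20 scored children per arm. That is in line with the interim count in section 15 (27 with a determined outcome plus 17 in follow-up, 44 in all) and with the loss of children too young to answer.

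**The plan's own figure.** For 75% against 50%, two-sided alpha 0.05 and 90% power, the standard two-proportion formula gives 77 per arm, and the log relative risk with pooled null variance gives 80.0. Exact power of the log-RR Wald test at 79 per arm is 0.903. The unpooled closed form gives 85.2, but the other results support 79. Dropout: 79/0.9 = 87.8, so 88 per arm and 176 in total. The figure is reproduced and serves here only as the base sample size.

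**Large-sample gain.** Adjusting for baseline multiplies the variance of the difference by 1 - r². The detectable difference is for 80% power at two-sided 0.05: (1.960 + 0.842) × √(2(1 - r²)/79), in SD units. Power is for an assumed true difference of 0.45 SD.

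| r (assumed) | Variance factor | Equivalent n per arm, 79/(1 - r²) | Detectable difference (SD) | Power at 0.45 SD |
|---|---|---|---|---|
| t-test | 1 | 79 | 0.446 | 80.7% |
| 0.3 | 0.91 | 86.8 | 0.425 | 84.3% |
| 0.5 | 0.75 | 105.3 | 0.386 | 90.4% |
| 0.6 | 0.64 | 123.4 | 0.357 | 94.2% |

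A simulation at 79 per arm (20,000 replicates) gave variance ratios of 0.917 at r = 0.3 and 0.760 at r = 0.5, against 0.91 and 0.75 from the formula.

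**Small-sample correction.** Estimating one covariate slope multiplies the adjusted variance by 1 + 1/(2n - 4). At 20 per arm this is 1 + 1/36 = 1.028:
- r = 0.3: 0.91 × 1.028 = 0.935, a reduction of 6-7%
- r = 0.5: 0.75 × 1.028 = 0.771, a reduction of 23%
- r = 0.6: 0.64 × 1.028 = 0.658, a reduction of 34%

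Adding the three-level weight stratum makes three covariate terms, with a factor of 1 + 3/34 = 1.088. If weight is unrelated to the score, the reductions fall to about 1%, 18% and 30%.

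**Bias and chance imbalance.** With a true difference of 0.45 SD, both methods averaged 0.45 over the simulated randomizations, so the t-test is unbiased. Among replicates where the arms differed by about 0.3 SD at baseline, the t-test averaged 0.535 (r = 0.3) and 0.606 (r = 0.5), while the adjusted estimate averaged 0.447 and 0.462. In points, with an assumed SD of 2, the standard error of the chance baseline difference is 2 × √(2/79) = 0.32 at 79 per arm and 2 × √(2/20) = 0.63 at 20 per arm. A fraction r of any such difference enters the unadjusted estimate.

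**The case against.** The strongest reply is that the planned test is valid and little rests on it. Allocation is randomized 1:1, so the difference in follow-up means is unbiased. Section 10.1 already labels the comparison exploratory, and both the sample size and the rejection rule concern the primary relative risk. All of this stands and keeps the point modest. It does not remove the gain, because the reasons given for the label are missing visits and young age, not baseline differences, and p-values will still be reported.

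A second reply is that the schedule row names no scale, and that section 5.2 says the EQ-5D-Y is completed at every visit. This also stands in part. Quality of My Life at baseline is the likely reading, since the same row covers the follow-up visits and section 5.2 has outcomes assessed at all visits, but the sponsor must confirm it.

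Three stronger readings might be inferred, and the SAP supports none of them:
- **The t-test confounds treatment with severity at entry.** It does not do so systematically. The exposure is to chance imbalance and extra variance.
- **The plan ignores baseline severity.** Section 8.3 checks "active joint count, physician global assessment of disease activity, parent global assessment of wellbeing" among others. The fault is that the named model cannot act on a continuous outcome.
- **The parent-proxy EQ-5D-Y ought to be compared between arms to cover younger children.** Sections 5.1 and 5.2 collect it for a future cost-effectiveness analysis, so leaving it out of the efficacy comparisons fits its stated purpose.

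**Conclusion.** The point holds as a low-cost improvement together with a gap in the wording of the adjustment rule. It is not an error that invalidates a result. The unadjusted test gives up precision that a baseline score would recover: about 9%, 25% or 36% of the variance at 79 per arm for r of 0.3, 0.5 or 0.6, and slightly less at 20 per arm. These sizes rest on assumed correlations, and the 20 per arm is also assumed. The whole point depends on the baseline questionnaire being Quality of My Life. At the low end of the range the gain is small. That logistic regression is the only adjustment model offered for a continuous score follows from the text and needs no assumption.

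**What to change.** 1. Confirm that the baseline entry in section 6.4 includes Quality of My Life.
2. In section 10.1, replace the t-test for this endpoint with a linear model of the 4-8 month score on arm and baseline score, and report the adjusted mean difference with its confidence interval. Keep the exploratory label. Do not add weight stratum by default, since at small numbers it can use up most of the gain.
3. Where a child has a 4-8 month score but no baseline score, use the multiple imputation already planned in section 8.4, which excludes only MISS scores.
4. In sections 8.3 and 10, state that linear regression is used to adjust continuous outcomes and keep logistic regression for binary ones.
5. Record in section 15 that the change was made after the interim analysis. The trial is open-label and the interim report lists efficacy outcomes by arm, so the model should be fixed and dated before the final data are analysed.

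The cost is SAP wording and one regression model. No new data are needed.

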6.1 General Study Design and Plan

(ICH E3;9) (ICH E3; 9.2, 9.7.1, 11.4.2.7. ICH E9; 3.3.2)

Children (ages 4-16 years) in the CAPRI JIA Registry who are starting methotrexate for the first time are eligible to participate in OPT-JIA. The target sample is 176 children followed for one year after starting methotrexate. Patients are followed every 1-4 months as clinically indicated. Outcomes are assessed via online data collection into the Registry at all clinic visits. The OPT-JIA protocol calls for an interim efficacy analysis completed after 90 children are recruited. The analysis results are to be used by an independent data and safety committee (DSC) to review for any needed adjustments to the target sample size, or study termination for success or futility.

OPT-JIA is a CAPRI JIA Registry-based pragmatic adaptive superiority RCT. OPT-JIA trial schema is reproduced in Figure 1 below.

Registry-based: The trial uses infrastructure already in place for the CAPRI JIA Registry [8].

Pragmatic: Broad inclusion criteria and simple outcome assessments compatible with usual care.

Adaptive: OPT-JIA is a Planned Sample-Size Re-Estimation Adaptive Trial as described by Bhatt & Metha [9].

Superiority: Designed to test superiority (as opposed to non-inferiority) of ondansetron premedication.

RCT: Treatments assigned by block randomization and analyses adjusted for post-randomization imbalances. Patients are randomized online via the REDCap [10] Registry plug-in using a 1:1 block randomization by Canadian region of residence and patient weight (<15Kg, 15-30Kg, >30Kg) with randomly assigned block size to ensure allocation concealment [11]. There is no blinding.

[figure not shown]

Figure 1: Trial schema for the Ondansetron Premedication Trial in Juvenile Idiopathic Arthritis (OPT-JIA).

Children in the intervention group are prescribed premedication with oral ondansetron (2 mg if <15Kg, 4 mg if 15-30Kg, 8 mg if >30Kg) to be taken one hour before each weekly methotrexate dose, followed by two additional doses every 6-8 hours if awake. All children receive methotrexate and folic/folinic acid as per the rheumatologist's usual practice. Current North American guidelines recommend a dose of methotrexate of 10-20 mg/m² weekly subcutaneously or orally to a maximum of 25mg/week, at the discretion of physician and family [12, 13]. Folic/folinic acid is commonly used as 1mg orally daily or 5-10mg orally weekly.

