8.2 Analysis Populations

(ICH E3; 9.7.1, 11.4.2.5. ICH E9; 5.2)

The primary analysis will be conducted on the intention-to-treat population, including all randomized subjects. A secondary per-protocol analysis will be conducted on those subjects who received the assigned intervention for at least 3 months (ondansetron and methotrexate in the intervention group, methotrexate in the control group). Because it was clear at the time of interim analysis that some patients stopped methotrexate before 3 months due to intolerance, the per protocol analysis was modified to also include patients who stopped the medication before 3 months due to intolerance or toxicity.

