8.4 Missing Data

(ICH E3; 9.7.1, 11.4.2.2. ICH E9;5.3. EMA Guideline on Missing Data in Confirmatory Clinical Trials)

During ongoing quality control of data entered in the study database, data from a study visit is reviewed by the study registry coordinator within 2 weeks of being entered and queries are sent to the site regarding any missing or apparently spurious data. Once these queries are answered satisfactorily, the data for that visit is locked. Only data contained in locked visits will be used for trial analyses.

In preparation for the interim and final analyses, the study statistician will perform further examination of the data for outlier values. Values outside a plausible range (e.g. an erythrocyte sedimentation rate >200 mm/h) will be converted to missing values.

After receiving the locked study dataset for the final analysis and dealing with values outside a plausible range, missing values will be imputed if needed using multiple imputations by chained equations.

Missing MISS questionnaire scores will not be imputed. Subjects with missing MISS questionnaire scores while still receiving methotrexate will be considered as censored as of the last available visit with a valid MISS score.

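### The 4-8 month mean MISS is compared only in children with a score, with no rule for those who stopped methotrexate earlier for intolerance, so it may be biased in a direction the SAP leaves open

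*SAP*

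**What the plan says.** Mean MISS at 4-8 months is a secondary endpoint (SAP section 5.2). Section 6.4 sets its window at days 120 to 240. Section 10.1 selects the score ("If more than one score is available 4-8 months after enrollment, the score closest to 26 weeks is used") and gives the test: "The mean scores of intervention and control groups will be compared with a two-sample two-tailed t-test". The same test is planned for Quality of My Life.

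On missing scores, section 8.4 says: "Missing MISS questionnaire scores will not be imputed". Its one handling rule is: "Subjects with missing MISS questionnaire scores while still receiving methotrexate will be considered as censored as of the last available visit". That covers only children still on methotrexate. Censoring also suits the Kaplan-Meier endpoints but means nothing for a mean score.

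Section 8.2 reports from the interim analysis that "some patients stopped methotrexate before 3 months due to intolerance". It gives no number and no split by arm. Section 6.2 adds that children who stop methotrexate also stop ondansetron.

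Section 10 sets the analysis population as an "intention to treat analysis including all randomized participants irrespective of whether they completed the trial", and section 6.1 says: "Outcomes are assessed via online data collection into the Registry at all clinic visits".

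Section 10.1 also says: "Mean scores and between groups p-values at 26 weeks are exploratory and will be interpreted with caution for two reasons". The two reasons are the lack of fixed-time visits and, for Quality of My Life, children too young to answer. Mock Table 4 still gives mean MISS a mean difference, a confidence interval and a p value.

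**The concern.** A child who stops methotrexate for intolerance before 3 months has done so before day 120. In the window that child either has no MISS or has one recorded on neither methotrexate nor ondansetron. In both cases some of the worst experience on the drug drops out of the mean. Whether a child contributes an on-drug score then depends on what the score measures, and possibly on the assigned arm. Randomization no longer protects the comparison.

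Both stated cautions describe missingness from visit timing or age. Neither tells the reader that a score may be absent because the child could not tolerate the drug. The sponsor saw the same problem elsewhere: the per-protocol set was changed to keep these children, and the primary endpoint counts stopping methotrexate as failure. Section 10.2 applies that modified set to the secondary endpoints too, so it re-admits children who have no on-drug 4-8 month score to give.

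At stake is a row of Table 4 that could appear to contradict, or to reinforce, the primary result merely because of who was scored.

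**Working it through.** **The plan's own figures.** The SAP states no mean, SD, target difference or expected missing share for MISS. Its one design figure, 79 evaluable per group (section 7), is for the primary relative risk. The log-RR formula with pooled null variance gives [1.960·√(2·0.375/0.625) + 1.2816·√(0.25/0.75 + 0.5/0.5)]² / (ln 1.5)² = 80.0, close to 79. Dropout: 158/0.9 = 175.6, so 176. Here 79 serves only as a group size.

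**Assumed inputs.**
- Intolerant share p: 25% intervention and 50% control, treating every failure in section 7 as intolerance. As an alternative for control, 41.5% (59/142, from the cohort in section 8.5.4).
- Mean MISS: 2 in tolerant children; M = 10 to 14 in intolerant children.
- A share s of intolerant children, unrelated to their score, has no window score. All tolerant children are scored.

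**Stoppers unscored.** The intolerant share among scored children is q = p(1−s)/(1−ps), and the arm mean is 2 + (M−2)q. The full difference is (M−2)·0.25, or 2.0 to 3.0 points. The fraction retained is (q_C − q_I)/(p_C − p_I), which does not depend on M.

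| Lost: intervention / control | q_I | q_C (p_C = 50%) | Retained | Retained if p_C = 41.5% |
|---|---|---|---|---|
| 10% / 10% | 0.231 | 0.474 | 97% | 96% |
| 40% / 40% | 0.167 | 0.375 | 83% | 80% |
| 20% / 40% | 0.211 | 0.375 | 66% | 53% |
| 40% / 20% | 0.167 | 0.444 | 111% | 118% |
| 60% / 10% | 0.118 | 0.474 | 142% | 165% |

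**Where the direction turns.** With p_C = 50% and 20% lost in control, the bias is zero when q_I = 0.444 − 0.25 = 0.194. Then s_I = (0.25 − 0.194)/(0.25·(1 − 0.194)) ≈ 0.28. Below about 28% lost in the intervention arm the difference is understated; above it, overstated.

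**Stoppers scored 0 off drug.** The arm mean is 2(1−p) + M·p(1−s). With p_C = 50% and equal shares of 10% to 40%, 88% down to 50% is retained. At 20%/40% it is 25% to 30%; at 60%/10% it is 147% to 150%.

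**No true difference (50% intolerant in both arms, M = 12).** Equal loss gives no bias. Losses of 20% and 40% create a false difference of 10·(0.444 − 0.375) ≈ 0.7 points.

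**Simulated power.** 79 per arm, 3,000 runs per setting, intolerant mean about 12, shares 25% and 50%. A t-test with every child scored has power 0.82 to 0.84.

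| Lost: intervention / control | Complete-case t-test | Worst-rank Wilcoxon |
|---|---|---|
| 20% / 20% | 0.78 | 0.79 |
| 40% / 40% | 0.70 | 0.79 |
| 20% / 40% | 0.46 | 0.85 |
| 40% / 20% | 0.91 | 0.71 |

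With no true MISS difference and unequal loss, the complete-case test rejects in about 10% to 12% of runs. The worst-rank test rejects in 8% to 9%, because it counts the unequal stopping as a difference. In a second model (skewed scores, means 6.0 and 4.2, stopping more likely at higher scores), power ran from about 20% to 74% for the t-test and about 30% to 81% for worst rank. In one setting worst rank was slightly the weaker (69% against 73%). These figures are illustrative only.

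**Quality of My Life.** Adjusting for baseline multiplies the variance of the difference by about 1 − r². The correlation r is not given; for assumed r of 0.3, 0.5 and 0.7 the factor is 0.91, 0.75 and 0.51.

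**The case against.** The strongest reply has four parts.

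- **Stoppers need not have left.** A reader might infer that children who stop early are gone by day 120. The SAP does not say so: outcomes are collected at every clinic visit, MISS is scheduled at every visit, and all randomized children are in the analysis. This stands. It changes the problem without removing it, since a later score is then an off-drug score with no rule attached. The questionnaire's wording is not in the text at hand, so what such a score measures is open.
- **The direction is not established.** A reader might also infer that the comparison understates the benefit of premedication. That needs intolerant control children to be lost about as often as intolerant intervention children, or more often. Section 6.1 lets control children with nausea or vomiting receive ondansetron, which could keep some of them on methotrexate and tilt the loss the other way. This stands.
- **The endpoint is already hedged.** It is labelled exploratory, and early stopping and early MISS of 6 or more are captured by the primary and Kaplan-Meier endpoints. This limits the weight of the point, but the caution given names the wrong source of missingness.
- **Worst rank changes the question.** It turns a mean score into a composite that partly repeats the primary endpoint, and ranking toxicity stoppers worst would score events such as abnormal liver tests as MISS symptoms. This stands, and is why the test belongs in a sensitivity analysis restricted to intolerance.

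**Conclusion.** The point holds as a gap in definition with a possible bias. The comparison is complete-case, some children stopped for intolerance before the window, no rule covers their scores, and the stated cautions omit this mechanism. Bias toward no difference is the likelier result if intolerant control children stop as often as, or more often than, intolerant intervention children. The firmer claim of understatement is not supported, because the SAP gives no stopping rates by arm.

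With stoppers unscored, the scenarios run from 53% to 165% of the full difference. All rest on assumed intolerant shares and losses, and the power figures also on assumed score distributions. None is an estimate for this trial. The consequence is minor: one exploratory comparison, with the primary endpoint untouched.

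The Quality of My Life suggestion is separate. The unadjusted t-test is not wrong; adjustment is simply more precise.

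**What to change.** In section 10.1:

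- Keep the mean MISS difference as the exploratory estimate, described as on-treatment among children scored.
- State that a MISS recorded after methotrexate has been stopped is not used as an on-treatment score. Say how temporary holds are treated; section 10.1 already separates them from stopping.
- Report by arm the number scored in the window and the number who stopped methotrexate early for intolerance.
- Add a sensitivity Wilcoxon rank-sum test giving the worst rank to children who stopped methotrexate for intolerance before their window score. Do not include those who stopped for unrelated toxicity. Note that it also responds to a difference in stopping.
- Add missing scores caused by stopping for intolerance as a third reason for caution.

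Separately, compare Quality of My Life at 4-8 months by ANCOVA on its baseline score. This assumes that the baseline quality-of-life questionnaire in section 6.4 includes that scale.

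The cost is a few sentences, two counts per arm, one extra test and one changed model. No new data collection is needed. Any simulated power quoted in support should be given as a range or left out.
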